9.3.1. Inclusion Criteria

[figure not shown]
Evidence of a personally signed and dated informed consent document indicating that the patient (or a legally acceptable representative) has been informed of all pertinent aspects of the study.

Participants who meet all the following criteria will be eligible for enrollment in this study:

1. Willing and able to provide written informed consent (aged ≥ 18 years), parental/guardian consent and participant assent (aged ≥ 12 to <18 years) per local regulations, or pediatric participants (aged 4 to <12 years) with parental/guardian consent per Institutional Review Board (IRB) policy and requirements, consistent with ICH guidelines
2. Male or female participants with documented diagnosis of sickle cell disease (all genotypes)
3. Participants who are currently taking Oxbryta® (Voxelotor) or have been prescribed and will initiate treatment with Oxbryta® (Voxelotor) according to the Oxbryta® (Voxelotor) USPI

When participants have been prescribed Oxbryta® (Voxelotor) and deemed eligible to participate in the registry study based on the inclusion/exclusion criteria, they will be enrolled in the study regardless of whether they have started taking Oxbryta® (Voxelotor). After enrollment into the study, it is recommended that the site perform the pre-Oxbryta® (Voxelotor) participant assessments as soon as possible. Once the first dose of Oxbryta® (Voxelotor) treatment has been administered, the participants will be followed for up to 5 years. Patient enrollment process flow is in [Figure 2](#).

Figure 2. Enrollment Process Flow

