4.2. Study populations

All participants at each participating study site who have been treated with Oxbryta® (Voxelotor) or have been prescribed and will initiate treatment with Oxbryta® (Voxelotor) according to the Oxbryta® (Voxelotor) USPI will be considered for inclusion in this study.

Population	Description
Full analysis set	Participants met inclusion/exclusion criteria and signed the informed consent including screen failures (participants who did not receive Oxbryta within 6 months of the informed consent date).
Safety analysis set	Participants were in the Full analysis set and received at least one dose of Oxbryta including participants who received at least one dose of Oxbryta in C5341018 (RETRO) study.

When participants have been prescribed Oxbryta® (Voxelotor) and deemed eligible to participate in the registry study based on the inclusion/exclusion criteria, they will be enrolled in the study regardless of whether they have started taking Oxbryta® (Voxelotor). After enrollment into the study, it is recommended that the site perform the pre-Oxbryta® (Voxelotor) participant assessments as soon as possible. Once the first dose of Oxbryta® (Voxelotor) treatment has been administered, the participants will be followed for up to 5 years. Patient enrollment process flow is shown in Figure 2.

Figure 2. Enrollment Process Flow

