4.7. Statistical methodology and analyses

The following general analysis will be followed for this study, unless otherwise specified.

Unless otherwise specified, continuous/quantitative variables will be summarized using descriptive statistics which will include the number of participants with data to be summarized (n), mean, standard deviation (SD), median, first and third quartile (Q1, Q3), minimum, maximum, and the number of missing observations. Minimum and maximum will be reported with the same number of decimal places as collected in raw data, while mean, median, Q1, Q3 will be reported with one extra decimal place, and SD will be reported with two extra decimal places. Descriptive statistics for categorical/qualitative variables will be presented with number of participants and percentage (%) of participants in each category.

Percentages will not include the missing category and will be calculated over the number of participants with available (non-missing) data. A category with a zero count will be presented as “0” and a category with a 100 percentage will be displayed as “100”.

The annualized incidence rate is defined as total numbers of a given event for all participants divided by the total patient-year where the total patient-year is defined as the sum of total duration (years) as defined in the Section 4.7.1 for all participants.

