4.7.1. Index date and follow-up

The index date is defined as the inform consent date. The Post Oxbryta period is from the first dose of Oxbryta to the date of end of treatment or end of study.

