- Change from pre-Oxbryta treatment period in the following Chemistry parameters corresponding to treatment with Oxbryta® (Voxelotol):
 - Ferritin

Analysis: Observed and change from pre-Oxbryta treatment period on ferritin will be summarized descriptively ([Section 4.7](#)) by visit.

- Change from pre-Oxbryta® (Voxelotol) treatment period in renal function:
 - Creatinine (Serum)
 - Albuminuria (urine albumin/creatinine ratio [ACR])
 - Hemoglobinuria (urine dipstick positive for blood +1 or greater and ≤ 2 RBC by high power field)
 - Serum cystatin C
 - Estimated eGFR calculated using the CKD-EPI equation

Analysis: Observed and change from pre-Oxbryta treatment period on Creatinine (Serum), Albuminuria, Hemoglobinuria, Serum cystatin C and eGFR will be summarized descriptively ([Section 4.7](#)) by visit

- Rate of SCD complications including acute pain crisis, acute chest syndrome

(ACS), priapism, stroke, and transient ischemic attack (TIA), chronic or end stage kidney disease, iron overload, leg ulcers, cardiac malfunction, and pulmonary hypertension (PH) and RBC transfusions.

Analysis:

The number and percentage of participants with SCD complications including acute pain crisis, ACS, priapism, stroke, chronic or end stage kidney disease iron overload, leg ulcers, cardiac malfunction and PH and RBC transfusions will be summarized by SOC and PT throughout the treatment period.

The annualized incidence rate of SCD complications including acute pain crisis, ACS, priapism, stroke, chronic or end stage kidney disease iron overload, leg ulcers, cardiac malfunction and PH and RBC transfusions will be summarized by SOC and PT throughout the treatment period.

- **PGIC**

PGIC includes 7 response categories: Very much improved, much improved, minimally improved, no change, minimally worse, much worse and very much worse.

Analysis: The PGIC will be summarized as numbers and percentages by visit for each response category.

- **CGIC**

CGIC includes 7 response categories: Very much improved, much improved, minimally improved, no change, minimally worse, much worse and very much worse.

Analysis: The CGIC will be summarized as numbers and percentages by visit for each response category.

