6. APPENDICES

6.1. Appendix A: List of tables

Table/Listing	Title	Endpoint
Table 15.1.1	Summary of Participant Disposition - Full Analysis Set	Disposition
Table 15.1.2	Demographics and Baseline Characteristics - Full Analysis Set	Baseline
Table 15.1.3	Medical History – Full Analysis Set	Medical history

Table 15.1.4	Study Drug Administration - Safety Analysis Set	Exposure
Table 15.1.5	Study Drug Administration and Dosage Changes Initiated by the Physician - Safety Analysis Set	Exposure
Table 15.2.1	Change in Hematologic Laboratory -Hb Tests by Visit - Full Analysis Set	Effectiveness
Table 15.2.2	Change in Hematologic Laboratory -Hemolysis measures by Visit - Full Analysis Set	Effectiveness
Table 15.2.3	Change in Chemistry Laboratory - Chemistry measures by Visit - Full Analysis Set	Effectiveness
Table 15.2.4	Change in Renal Function Laboratory Tests by Visit - Full Analysis Set	Effectiveness
Table 15.2.5	Summary of SCD Complications-Full Analysis Set	Effectiveness
Table 15.2.5.1	Summary of Transfusions -Full Analysis Set	Effectiveness
Table 15.2.6	Annualized Incidence Rate of SCD Complications - Safety Analysis Set	Effectiveness
Table 15.2.6.1	Annualized Incidence Rate of Transfusions - Safety Analysis Set	Effectiveness
Table 15.2.7	Summary of Patient Global Impression of Change (PGIC) – Full Analysis Set	HRQoL
Table 15.2.8	Summary of Clinical Global Impression of Change (CGIC) – Full Analysis Set	HRQoL
Table 15.3.1	Treatment Emergent Adverse Events by System Organ Class and Preferred Term by Severity - Safety Analysis Set	Safety
Table 15.3.2	Treatment Related Treatment Emergent Adverse Events by System Organ Class and Preferred Term by Severity- Safety Analysis Set	Safety

Table 15.3.3	Treatment Emergent Serious Adverse Events by System Organ Class and Preferred Term by Severity - Safety Analysis Set	Safety
Table 15.3.4	Pregnancy Outcomes and Fertility listings - Safety Analysis Set	Safety
Table 15.3.5	Individual Listings of Deaths- Safety Analysis Set	Safety
Table 15.3.6	Listing of AEs Leading to Discontinuation of the Study - Safety Analysis Set	Safety
Table 15.3.7	Individual Listing of SAEs - Safety Analysis Set	Safety
Table 15.4	Listing of Concomitant Medication - Safety Analysis Set	Concomitant Medication
Table 15.5.1	Annualized Incidence Rate of Acute Pain Crisis – Safety Analysis Set (With Chronic Pain)	Subgroup
Table 15.5.2	Annualized Incidence Rate of Acute Pain Crisis – Safety Analysis Set (Without Chronic Pain)	Subgroup

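### The annualized priapism rate uses the patient-years of both sexes, so it is a whole-cohort rate that understates the rate in males by the female share of patient-years

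*SAP*

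**What the plan says.** SAP 4.7 gives a single definition for all annualized rates: "total numbers of a given event for all participants divided by the total patient-year". It defines the total patient-years as "the sum of total duration (years) as defined in the Section 4.7.1 for all participants". Section 4.7.1 supplies the duration: "The Post Oxbryta period is from the first dose of Oxbryta to the date of end of treatment or end of study". Neither text refers to sex or to being at risk of the particular event.

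SAP 4.7.3 then plans "The annualized incidence rate of SCD complications including acute pain crisis, ACS, priapism, stroke" and further complications, after planning the number and percentage of participants with each of them. The rate table is 15.2.6, "Annualized Incidence Rate of SCD Complications - Safety Analysis Set". SAP 4.2 defines that set as follows: "Participants were in the Full analysis set and received at least one dose of Oxbryta", with no sex criterion. The percentage table, 15.2.5, uses the Full Analysis Set, which has none either.

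Protocol 9.3.1 admits both sexes: "Male or female participants with documented diagnosis of sickle cell disease (all genotypes)". Sex is a listed demographic variable in SAP 4.3.

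**The concern.** Priapism can occur only in males. Female follow-up adds to the denominator and can add nothing to the numerator, so the reported figure depends on the sex mix of the registry as well as on how often the event occurs. Two cohorts with the same rate in males would report different priapism rates if their female shares differed.

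Priapism is named among the effectiveness endpoints in Protocol 8.1.1.2 and SAP 3.2. SAP 4.7.3 makes SCD-related clinical events one focus of the abbreviated study report. Neither the rate definition nor the table titles tell the reader that the priapism row includes people who are not at risk, so the figure is likely to be read as a risk in males.

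**Working it through.** **Is there an override?** SAP 4.7 lets later sections depart from its general rules, so I looked for a departure.

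- SAP 4.7.1 (follow-up): no sex-specific duration.
- SAP 4.7.2 (risk windows): marked not applicable.
- SAP 4.2.1 and 4.7.5 (subgroups): chronic pain, maximum Hb increase, and availability of pre-treatment complication or adverse event data. None is by sex.
- SAP Appendix A (table list): no male-only table or denominator.
- Protocol 9.11.3 (analysis) and 10.3.6.1.4 (priapism data): no restriction.

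By contrast, the protocol's schedule of activities does limit an item by sex where that is intended: pregnancy tests apply only to females of child-bearing potential.

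**Rate.** The documents state no priapism rate and no sex split, so there is no plan figure to reproduce. Let E be the number of priapism events (all in males), PYm and PYf the male and female patient-years, and f = PYf/(PYm + PYf).

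- Rate under the SAP = E/(PYm + PYf)
- Rate in those at risk = E/PYm
- SAP rate / at-risk rate = PYm/(PYm + PYf) = 1 − f

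The relative understatement is therefore f itself, whatever the event rate or length of follow-up. The values of f below are assumptions:

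| Female share of patient-years, f | SAP rate / male rate | Multiplier to get the male rate, 1/(1 − f) |
|---|---|---|
| 0.30 | 0.70 | 1.43 |
| 0.40 | 0.60 | 1.67 |
| 0.50 | 0.50 | 2.00 |
| 0.60 | 0.40 | 2.50 |
| 0.70 | 0.30 | 3.33 |

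Numerical check, using the planned 500 participants and assuming 2 years each, f = 0.50 and a male rate of 0.10 per patient-year: total patient-years = 500 × 2 = 1000; male patient-years = 500; E = 0.10 × 500 = 50. The SAP rate is 50/1000 = 0.050, and the male rate is 50/500 = 0.100. With 5 years each, the ratio is the same.

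**Patient-years or headcount?** The share that matters for the rate is that of patient-years. With 50% females by headcount, mean follow-up of 2 years in females and 3 in males gives f = (0.5 × 2)/(0.5 × 2 + 0.5 × 3) = 0.40. Reversing the two durations gives 0.60.

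**Percentage.** SAP 4.7 takes percentages over participants with non-missing data, and nothing says that females count as missing for priapism. If h is the female headcount share in that denominator, the reported percentage is (1 − h) times the male percentage.

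**Can a reader undo it?** For the percentage, yes. Tables 15.2.5 and 15.1.2 both use the Full Analysis Set, so the number with priapism can be divided by the number of males. For the rate, not exactly, because patient-years by sex are not among the listed outputs. The headcount split gives an approximation if follow-up is similar in the two sexes.

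**The case against.** The strongest reply is that nothing is miscalculated. The SAP states openly that the denominator is everyone's follow-up, which gives a legitimate crude rate for the cohort, and it never calls the result a rate in those at risk. A table by system organ class and preferred term normally uses one denominator for all rows. This stands: the fault lies in what the figure conveys, and the arithmetic is sound. It does not remove the point, because the plan fixes a rule whose result for this one row is uninformative without the sex mix, and no label says so.

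The consequence is also limited. Priapism is one of about ten example complications, the analysis is descriptive, there is no formal sample size calculation, and no decision rests on this row. That stands too, and it sets the rank.

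A reader might go further and infer that a before-and-after comparison of priapism is biased. The documents do not support that. SAP 4.7.5 plans explicit pre/post rates only for acute pain crisis/VOC. SAP 4.7.3 plans the complication rates over the treatment period. Protocol 9.11.3 mentions comparison with the period before the first dose only where appropriate. A ratio would in any case be unaffected if the sex mix of patient-years were the same in both periods, and nothing suggests that it differs.

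A reader might also infer that the output cannot be compared with any male-based figure. That is too strong, because the male percentage can be recovered as shown above.

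**Conclusion.** The point holds as a minor one. Applied as written, SAP 4.7 and 4.7.3 give a crude whole-cohort priapism rate that understates the rate in males by exactly the female share of patient-years. Direction and formula follow from the SAP text and from the event being confined to males. The size does not: it rests on an assumed sex split, and the reported rate is 0.6 to 0.4 of the male rate for female shares of 40% to 60%. The percentage is diluted by the female headcount share but is recoverable; the rate is recoverable only approximately. No other endpoint is affected by this point.

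**What to change.** Add one sentence to SAP 4.7 or 4.7.3: for priapism, the percentage uses male participants as denominator and the annualized rate uses male patient-years. Footnote Tables 15.2.5 and 15.2.6 accordingly, giving the number of males and the male patient-years. Event counts stay as they are.

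The cost is one filter on a variable already collected, and one row whose denominator differs from the rest of its table; the footnote deals with the latter. If a uniform denominator is preferred, the least that is needed is a footnote that labels the priapism row as a whole-cohort figure and reports male patient-years, so that a reader can convert it.

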4.7.1. Index date and follow-up

The index date is defined as the inform consent date. The Post Oxbryta period is from the first dose of Oxbryta to the date of end of treatment or end of study.

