4. RESEARCH METHODS

4.1. Study design

This registry is an observational study designed to evaluate the effect of Oxbryta® (Voxelotor) in individuals with SCD. This registry is intended to benefit and support interests of participants, clinicians, regulatory bodies, payers, and industry by obtaining longitudinal data on Oxbryta® (Voxelotor). Approximately 500 participants with SCD who are prescribed and treated with Oxbryta® (Voxelotor) will be enrolled. The study will be conducted at approximately 35 sites in the US.

Any participant who is currently taking Oxbryta® (Voxelotor) or has been prescribed and will initiate treatment with Oxbryta® (Voxelotor), is eligible to participate. Eligible participants will receive treatment with Oxbryta® (Voxelotor) as prescribed by their physicians, as part of their usual care. Participants will be treated and evaluated per standard of care (SOC) and at the physician's discretion.

Participants will be introduced to the study by their health care team and will sign the informed consent form (ICF) or assent prior to any data collection for the study.

[figure not shown]
This study will collect data that are recorded in the participants' medical records and other secondary data sources such as Insurance and Pharmacy Claims. Study data will be collected at regular intervals (no more frequent than every 3 months) and entered in case report forms (CRFs) via an electronic data capture (EDC) system by the study staff.

Regardless of how long participants have been on Oxbryta® (Voxelotor) when they enroll in the study, participants will be followed for up to 5 years after their first dose of Oxbryta® (Voxelotor) treatment, or until they withdraw their consent to participate, or are discontinued from the study. Treatment, including interruptions and restarting treatment, will continue at the discretion of the treating physician, and there are no pre-defined treatment requirements. Participants may receive any additional medications prescribed by their treating physician or have any medical interventions that are deemed appropriate by the treating physician or study doctor. The participant or treating physician may discontinue Oxbryta® (Voxelotor) at any time. Participants who discontinue treatment with Oxbryta® (Voxelotor) earlier than 5 years will continue to be followed on study to collect clinical and health-related quality of life (HRQoL) outcomes for up to 5 years after their first dose of Oxbryta® (Voxelotor) treatment.

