4.7.4. Safety analysis

SCD complications are defined as 'Yes' to the question 'is this a SCD Complication' in the SCD complications/AE form while the other AEs are defined as 'No' to the question 'is this a SCD Complication' in the SCD complications/AE form.

All safety analyses will be based on safety analysis set (Section 4.2). The analysis period for Pre-Oxbryta is 12 months before the first dose of Oxbryta and the analysis period for post-Oxbryta is from the first dose of Oxbryta through end of the study or the date of dose pausing or treatment discontinuation if the date of end of study date is missing.

SAEs and protocol-specified AEs will be classified according to the Medical Dictionary for Regulatory Activities (MedDRA). The frequency of SCD complications and other AEs treatment-emergent adverse events (TEAEs) and treatment emergent SAEs will be tabulated by system organ class, preferred term, severity (and total), and relationship to Oxbryta® (Voxelotor) treatment. The pregnancy outcomes and fertility will be reported as a listing. Any events (including deaths) leading to discontinuation of the study and SAEs will be listed.

A TEAE is defined as an AE that occurs during the effective duration of treatment defined as the time from the first dose of Oxbryta through end of treatment date or the end of study completion/discontinuation date (if the date of end of treatment is missing) +28 days.

On the AE case report form there is a question “Did AE start prior to first dose?”

- If the response is “Yes” or the adverse event start date is missing, and the end date is prior to the first dose of Oxbryta, then the AE is not considered a TEAE
- If the response is “No” or “Unknown”, then the AE is considered a TEAE

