4.7.5. Subgroup analyses

Analysis: The annualized incidence rate (per patient year) of rate of ‘Acute Pain Crisis’ (SCD Complications) will be performed by Pre-Oxbryta and Post-Oxbryta.

Analysis subgroups:

- Chronic pain
 - a. participants with chronic pain
 - b. participants without chronic pain
- Maximum increase from Pre-Oxbryta in Hb
 - a. Full analysis set for participants with > 1 g/dL maximum increase from Pre-Oxbryta in Hb
 - b. Full analysis set for participants with <= 1 g/dL maximum increase from Pre-Oxbryta in Hb

Analysis: Annualized incidence VOC rate for pre-Oxbryta and post-Oxbryta will be reported.

The VOC event for Pre-Oxbryta is defined as 1) SCD complication with ‘Acute Pain Crisis’ in the Pre-Oxbryta SCD complication page or 2) any qualifying complications from SCD AE prior to Treatment Start Date.

The VOC event for Post-Oxbryta is defined as any qualifying complications from SCD AE on or after the treatment start date.

The qualifying complications from SCD AE are those that met at least one of the following two conditions:

- AE preferred term (AEDECOD) to be 'Sickle cell anaemia crisis';
- type of complications (CMPTYP) is 'Acute Pain Crisis'

- 1) Analysis population: Safety analysis set where participants had a non-missing Pre-Oxbryta SCD complications will be included in the analysis.
- 2) Analysis population: Safety analysis set where participants who had a non-missing Pre-Oxbryta SCD complications or participants who had an adverse events reported in Pre-Oxbryta or Post-Oxbryta will be included in the analysis.

Analysis: The annualized VOC incidence rate (per patient year) will be performed by Pre-Oxbryta and Post-Oxbryta.

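### Annualized rates take patient-years from SAP 4.7.1, but the event windows in 4.7.3, 4.7.4 and 4.7.5 differ, so at least one set of rates can mix windows

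*SAP*

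**What the plan says.** **Patient-years.** SAP 4.7 divides the total number of events by total patient-years, where "total patient-year is defined as the sum of total duration (years) as defined in the Section 4.7.1 for all participants". Section 4.7.1 then says: "The Post Oxbryta period is from the first dose of Oxbryta to the date of end of treatment or end of study". It gives no rule for choosing between the two dates and no pre-Oxbryta duration. Section 4.7.2, on risk windows, is marked not applicable.

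**Events.** Three sections set the post-Oxbryta window:

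- SAP 4.7.3, for annualized rates of SCD complications and transfusions: "RBC transfusions will be summarized by SOC and PT throughout the treatment period".
- SAP 4.7.4, for the safety analysis period: "from the first dose of Oxbryta through end of the study or the date of dose pausing or treatment discontinuation". The pausing or discontinuation date applies only if the end-of-study date is missing.
- SAP 4.7.5, for post-Oxbryta VOC: "any qualifying complications from SCD AE on or after the treatment start date". No end is stated.

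**Follow-up.** SAP 4.1 says: "Participants who discontinue treatment with Oxbryta® (Voxelotor) earlier than 5 years will continue to be followed on study", for up to 5 years after first dose. It also says: "Treatment, including interruptions and restarting treatment, will continue at the discretion of the treating physician".

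**Pre-Oxbryta period.** SAP 4.3 and 4.7.4 use the 12 months before first dose. The AE-form route to a pre-Oxbryta VOC in 4.7.5 is "any qualifying complications from SCD AE prior to Treatment Start Date", with no lower limit.

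**The concern.** A rate per patient-year means something only if events and time at risk are counted over the same window. Here one denominator serves several numerators whose windows differ, and the windows separate for exactly those participants who stop the drug early.

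Protocol 9.11.3 plans to compare event rates on Oxbryta with rates before the first dose. In the SAP, the pre/post acute pain crisis and VOC rates of 4.7.5 are what delivers that comparison for clinical events. If events run to end of study but patient-years stop with treatment, the post-Oxbryta rate is too high and a benefit can be hidden or reversed. If on-drug events are divided by full follow-up, the rate is too low and a benefit is exaggerated.

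**Working it through.** The SAP states no event rate, stopping rate or formal sample size calculation, so there is no figure to reproduce. The check has two parts.

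**1. Windows under each reading of 4.7.1**

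| Section (tables) | Event window as worded | If 4.7.1 means end of treatment | If 4.7.1 means end of study |
|---|---|---|---|
| 4.7.3 (15.2.6, 15.2.6.1) | Treatment period | Matches | Does not match: off-drug time, no off-drug events |
| 4.7.5 VOC (apparently 15.5.5) | From treatment start, no end | Does not match: off-drug events, no off-drug time | Matches |
| 4.7.5 acute pain crisis (15.5.1 to 15.5.4) | Post-Oxbryta only | Matches if 4.7.1 governs events, not if 4.7.4 does | Matches under either section |

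The first reading is the likelier. SAP 4.6 replaces an end-of-treatment date with end of study only when that date is missing or known to the year alone, and the TEAE rule in 4.7.4 likewise uses end of treatment first. Neither reading fits both 4.7.3 and 4.7.5 as written.

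**2. Size, under assumed stopping patterns**

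Let F be mean follow-up in years, T mean time on drug, and p the share stopping at 1 year. Then T = F − p(F − 1).

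- Equal event rates on and off drug: the upward mismatch multiplies the rate by F/T, the downward one by T/F.
- On-drug rate 0.70 of the pre-Oxbryta rate and off-drug rate 1.0: the upward mismatch reports (0.7T + F − T)/T, the downward one 0.7T/F.

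| F | p | T | F/T | T/F | Reported ratio, upward | Reported ratio, downward |
|---|---|---|---|---|---|---|
| 5 | 0.1 | 4.6 | 1.09 | 0.92 | 0.79 | 0.64 |
| 5 | 0.3 | 3.8 | 1.32 | 0.76 | 1.02 | 0.53 |
| 5 | 0.5 | 3.0 | 1.67 | 0.60 | 1.37 | 0.42 |
| 3 | 0.1 | 2.8 | 1.07 | 0.93 | 0.77 | 0.65 |
| 3 | 0.3 | 2.4 | 1.25 | 0.80 | 0.95 | 0.56 |
| 3 | 0.5 | 2.0 | 1.50 | 0.67 | 1.20 | 0.47 |

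Worked row (F = 5, p = 0.3): T = 5 − 0.3 × 4 = 3.8; upward (2.66 + 1.2)/3.8 = 1.02; downward 2.66/5 = 0.53.

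With matched windows the on-treatment ratio is 0.70 in every row. A matched full-follow-up ratio, (0.7T + F − T)/F, is 0.72, 0.77 or 0.82 for F = 5. If stopping comes at 2 years instead (F = 5), T = 4.7, 4.1 or 3.5 and F/T = 1.06, 1.22 or 1.43.

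**Two smaller gaps**

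- Because 4.7.1 gives no pre-Oxbryta duration, the denominator of the pre-Oxbryta rate is undefined where 4.7 says to find it. AE-form events earlier than 12 months before first dose, if any, could be counted over a 12-month denominator.
- For a missing end-of-study date, 4.6 uses the last known visit while 4.7.4 uses the pausing or discontinuation date.

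**The case against.** The strongest reply is that 4.7.5 defines which events qualify as VOC and separates pre from post at treatment start; it need not repeat an end date, because the post-Oxbryta period already has one in 4.7.1. If events are capped there and 4.7.1 is read as end of treatment, else end of study, then 4.7.1, 4.7.3 and 4.7.5 agree. That is a reasonable way to program it, and it is why the error is only possible. But the cap is unwritten, 4.7.1 still needs its own precedence rule, and 4.3 and 4.7.4 give the post-Oxbryta period a different end.

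Four further points limit the weight of the concern:

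- SAP 4.7.4 tabulates frequencies and listings, not rates. The direct conflict for rates is 4.7.3 against 4.7.5. Section 4.7.4 matters because it defines pre- and post-Oxbryta periods for the safety analysis set, which the titles of Tables 15.2.6, 15.2.6.1 and 15.5.1 to 15.5.5 name.
- The downward error needs the less likely reading of 4.7.1.
- A mean follow-up of 5 years may be out of reach. US approval was in November 2019 and the current SAP is dated 24 January 2025. If the data cut is near that date, which is not stated, the F = 3 rows are the better guide; there the ratio passes 1 only at 50% stopping.
- The rates are descriptive, the report is abbreviated, and Table 15.5.5 is labelled ad hoc. Its title refers to acute pain crisis, so its link to the VOC definition is inferred. Even so, SAP 4.7.3 says the limited efficacy data are to support the benefit-risk evaluation, and a descriptive rate still needs matched windows.

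On the pre-Oxbryta side, Protocol 10.3.6.1.2 already limits recorded pre-treatment complications to 12 months, so that gap is probably small.

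**Conclusion.** The concern holds. As worded, no single end date for 4.7.1 fits every event window, so at least one set of annualized rates can combine events and patient-years from different periods. The conflict in wording is clear; the resulting bias is possible, not certain, and depends on which reading is programmed.

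Its size cannot be taken from the documents. With 10% to 50% stopping at 1 year, mean follow-up of 3 or 5 years and equal on- and off-drug rates, the post-Oxbryta rate would be 1.07 to 1.67 times too high, or 0.60 to 0.93 of its true value. A reversal of benefit also requires the assumed 0.70 effect with full return to the pre-Oxbryta rate off drug, and either 50% stopping or, at 5 years of follow-up, 30%. This should be fixed before the rate tables are produced.

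**What to change.** In SAP 4.7.1, state one end date for each rate table and apply it to both events and patient-years:

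- **On-treatment rate:** first dose to the end-of-treatment date as imputed in 4.6, or end of study if still on drug. This fits the on-treatment comparison in Protocol 9.11.3.
- **Full-follow-up or off-treatment rate, if wanted:** a separate row with its own matched patient-years.
- **Interruptions and missing dates:** say whether interruption time stays in the patient-years, treat events during interruptions the same way, and say how events with a completely missing start date, which 4.6 leaves unimputed, are assigned.
- **Pre-Oxbryta period:** carry the 12 months into 4.7.1 and into the 4.7.5 rule for AE-form events, using the documented look-back where it is shorter.
- **Missing end-of-study date:** bring 4.7.4 into line with 4.6.

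The cost is SAP wording and table programming, with no new data. The on-treatment rate will rest on fewer events and patient-years than a full-follow-up rate.
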